17.1.2 Age percentiles for blood pressure in children

Source: 9

## Abbreviations

ADS	Analysis dataset
AE	adverse event
AUC	Area under the curve
BAY	sponsor's reference number for drugs
CV	Coefficient of variation
DMC	data monitoring committee
DVT	deep vein thrombosis
eGFR	estimated glomerular filtration rate
Hb	hemoglobin
i.e.	id est, that is
IxRS	interactive voice/web response system
MedDRA	Medical Dictionary for Regulatory Activities

mg	milligram
min	minute
ml	milliliter
PD	pharmacodynamics
PD	pharmacodynamics
PK	pharmacokinetic(s)
SAP	statistical analysis plan

## 1. Introduction

This SAP is based on the integrated clinical study protocol version 2.0 (21 Jul 2015) and its local amendment 2 for Canada dated 22 September 2015.

The goal of the rivaroxaban pediatric program is to make rivaroxaban available to children for treatment and secondary prevention of VTE. To accomplish this goal, an age- and body weight adjusted dosing regimen has been developed and is being evaluated in a phase III program in children from 6 months to less than 18 years.

Children between birth and less than 6 months will be evaluated within separate studies because of distinct differences in the coagulation system, presentation of venous thrombosis and treatment requirements.

In this phase I/II study, children with confirmed symptomatic or asymptomatic catheter related arterial or venous thrombosis will be treated for 7 days with the age- and body weight-adjusted rivaroxaban twice daily dosing regimen to achieve a similar exposure as that observed in adults treated for VTE with 20 mg rivaroxaban once daily.

Compared with adults, thrombosis is rare in children and often is a secondary complication of primary underlying medical conditions or of the use of central lines.

Treatment options are limited to heparins and VKA, which are cumbersome to manage due to the requirement for daily subcutaneous or intravenous injections and regular blood sampling for laboratory monitoring followed by dose adaptations. In children, the availability of an oral anticoagulant treatment that does not require subcutaneous or intravenous injections and regular blood sampling for laboratory monitoring, as is the case in adults, would be desirable.

To carefully allow for the evaluation of rivaroxaban in neonates and children younger than 6 months with confirmed symptomatic or asymptomatic catheter related arterial or venous thrombosis, we elected to evaluate the selected rivaroxaban dose regimen first in children that have been treated with anticoagulant therapy for at least two weeks. If this study reveals that the selected rivaroxaban dose regimen results in a similar exposure as that observed with 20 mg rivaroxaban in adults, and safety and efficacy is confirmed, a subsequent study will evaluate the selected rivaroxaban dose regimen for the acute and continued treatment of VTE.

## 2. Study Objectives

The primary objective is:

- to characterize the pharmacokinetic/pharmacodynamic profile of a 7-day treatment with oral rivaroxaban

The secondary objectives are:

- to assess the incidence of major bleeding and clinically relevant non-major bleeding
- to assess the incidence of symptomatic recurrent thromboembolism and
- to assess asymptomatic deterioration in the thrombotic burden on repeat imaging

**Table 2: Flow chart: pharmacokinetics and pharmacodynamics**

Pharmacokinetics and pharmacodynamics (PK/PD) a	Visit 1	Visit 2				Visit 3				Visit 4
Rivaroxaban treatment days	Screen day -10 to day 1	Treatment day 1		Treatment day 2		Treatment day 3		Treatment day 4 to 7		Day 8
Rivaroxaban administration		1 st dose	2 nd dose	1 st dose	2 nd dose	1 st dose	2 nd dose	1 st dose	2 nd dose	
PK/PD time points		0.5 to 1.5 hr post dose	2-4 hr post dose			2-8 hr post dose				10-16 hr after last dose at day 7
Obtain blood sample for PK b		•	•			•				•
Obtain blood sample for PD c			•			•				•

hr = hour(s), PD = pharmacodynamics, PK = pharmacokinetics

a The approximate total blood volume taken per child for PK/PD is 6.6 mL. Always draw the PD sample as the last sample.

b Blood volume per PK sample is approximately 0.6 mL; total blood volume for all PK samples is 2.4 mL.

c Blood volume per PD sample is approximately 1.4 mL; total blood volume for all PD samples is 4.2 mL.

## 4. General Statistical Considerations

### 4.1 General Principles

The statistical evaluation will be performed by using the software package SAS release 9.2 or higher (SAS Institute Inc., Cary, NC, USA). All variables will be analyzed by descriptive statistical methods. The number of data available and missing data, mean, standard deviation, minimum, median, and maximum will be calculated for metric data if not otherwise specified. Frequency tables will be generated for categorical data.

Summary statistics will be presented for the subjects under active treatment, data of subjects which did not receive any study medication will be listed only

The analysis datasets (ADS) standards for Xarelto will be applied.

### 4.2 Handling of Missing Data

Missing data will not be estimated by specific methods for imputation of data. Possible impact of missing values on the analysis will be discussed in the clinical study report.

All missing or partial data will be presented in the corresponding summary tables and in the subject data listing as they are recorded on the Case Report Form (CRF).

### 4.3 Interim Analyses and Data Monitoring

No interim analysis will be performed.

A data monitoring committee (DMC) has the responsibility to provide the steering committee with recommendations related to the protection of the children's safety, including stopping recruitment and study treatment. For that purpose, the DMC will regularly review all incidences of serious adverse events, recurrent venous or arterial thromboembolic events and bleeding, and PK/PD results.

#### 4.4 Data Rules

All reported medication intake by the children that stopped at least one day before the date of first study drug intake will be considered as previous medication, otherwise as concomitant medication.

Baseline is defined as the last observation prior to the first dose of study medication.

Arithmetic means will be calculated and used for tables and figures in case of repeated measurements for the same subject, timepoint, laboratory, and laboratory test.

In case of laboratory measurements from different laboratories with different normal ranges, ULN-normalized values will be calculated and used for tables and figures, if applicable. In case of missing upper limit of normal information, values will be listed only.

Phase I pool reference data for rivaroxaban plasma concentration, PT, and aPTT measurements to be used are given in

/by-sasp/patdb/projects/597939/xa\_ph1\_reports/stat/test\_epbka/pip/pip\_data.sas7bdat,

and by the corresponding high dose age groups of the Phase I pediatric study 12892 in

/by-sasp/patdb/projects/597939/12892/dm/prod/data/ad.

#### 4.5 Validity Review

The results of the Validity Review Meeting will be documented in the Validity Review Report and may comprise decisions and details relevant for statistical evaluation. Any relevant changes to the statistical analysis prompted by the results of the validity review meeting might be documented in an amendment or, if applicable, in a supplement to this SAP.

### 5. Analysis Sets

#### 5.1 Assignment of analysis sets

Final decisions regarding the assignment of subjects to analysis sets will be made during the Validity Review Meeting and documented in the Validity Review Report (see section 0).

**Full analysis set:** This analysis set will include all children from whom informed consent was obtained.

**Safety analysis set:** This analysis set will include all children who received at least one dose of rivaroxaban.

**Per protocol analysis set:** This population includes all children who completed the 7 day treatment period or had an efficacy or bleeding outcome before. This analysis set may exclude major protocol deviations.

**Listing only set (LoS):** this population includes all screening failures.

All subjects with at least 1 PK sample in accordance with the PK sampling strategy will be included in the PK analysis (PK analysis set).

All subjects with at least 1 blood sample for clotting parameters in accordance with the PD sampling strategy will be included in the PD analysis (PD analysis set).

## 6. Statistical Methodology

### 6.1 Demographic and other baseline characteristics

Summary statistics (arithmetic mean, standard deviation, median, minimum and maximum for quantitative variables) will be presented by total safety analysis set. Frequency tables for qualitative data will be provided. Medical history findings will be summarized using Medical Dictionary for Regulatory Activities (MedDRA) terms.

### 6.2 Safety analysis

#### Adverse events

All safety analyses will be performed on the safety population. The analysis will primarily focus on bleeding that occurred during or within 2 days after stop of rivaroxaban. Bleeding events observed later will be described separately. Individual listings of major and clinically relevant non-major bleeding will be provided. The incidence of bleeding will be summarized. If a sufficient number of bleeding events is observed, factors which potentially influence the occurrence of bleeding will be assessed by appropriate statistical procedures. Quantitative data will be described by the summary statistics and will be presented for the original data as well as for the difference to baseline. Frequency tables will be provided for qualitative data.

#### Safety parameters

Quantitative data (hematology, blood chemistry, pulse rate) will be described by the following summary statistics: arithmetic mean, standard deviation, median, minimum and maximum. These summary statistics will be presented for the original data, as well as for the difference to baseline. Frequency tables will be provided for qualitative data. Laboratory data outside the reference range will be listed and flagged with 'L' for low and 'H' for high. Additional tables with all abnormal values will be presented.

Graphical displays of individual data as well as mean values with standard deviation will be included.

### 6.3 Efficacy analysis

All efficacy analyses will be performed on the full analysis set population. The incidence of symptomatic recurrent venous thromboembolism and asymptomatic deterioration in thrombotic burden on repeat imaging will be summarized.

### 6.4 PK/PD analysis

#### Pharmacokinetic data

The concentration-times courses of rivaroxaban will be tabulated for each sampling interval. The following statistics will be calculated for each of the sampling intervals: arithmetic mean, standard deviation and coefficient of variation (CV), geometric mean, geometric standard deviation (re-transformed standard deviation of the logarithms) and CV, minimum, median, maximum value and the number of measurements. Means for any interval will only be calculated if at least 2/3 of the individual data were measured and were above the lower limit of quantification (LLOQ). For the calculation of the mean value a data point below LLOQ will be substituted by one half of this limit. In tables showing mean values, where values below LLOQ are included in the calculation of mean values, these means will be marked.

Individual and geometric mean concentration vs time curves of rivaroxaban (using the actual sampling times for individual plots and the planned sampling intervals for mean plots) will be plotted using both linear and semilogarithmic scale.

If applicable, pharmacokinetic characteristics derived via popPK modeling ( $t_{\max}$  excluded) will be summarized by the statistics mentioned above.  $t_{\max}$  will be described utilizing minimum, maximum and median as well as frequency counts.

Comparison with reference data will be graphically sketched.

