Dispense study medication Instruct how to administer the study medication Provide study booklet Provide rivaroxaban oral suspension handling guidelines		• ^c			
Record all concomitant medication		•	•	•	•
Collect baseline imaging ^d	•				
Repeat ultrasound imaging ^d		•		• ^e	
Check for study outcomes ^d			•	•	•
Check adverse events		•	•	•	•
Check drug accountability and compliance				•	
Check if anticoagulant treatment continued after Visit 4					•
Complete eCRF	•	•	•	•	•

ALT = alanine aminotransferase, eCRF = electronic case report form, Hb = hemoglobin; INR= international normalized ratio, VKA= vitamin K antagonist

^a The screening visit can be performed up to 10 days prior to inclusion into the study.

^b Hb, platelets, creatinine, ALT, total and direct bilirubin results should be available within 10 days prior to inclusion into the study. If results are not available, obtain blood sample.

^c If child discharged from the hospital.

^d Compile adjudication package and send it to the adjudication office.

^e Repeat ultrasound can be obtained on Day 8 ± 1.

^f INR should be below 2.5 before starting rivaroxaban (see Section 5.1.1.3).

¹⁶ The study flow chart was modified via Amendment 1 (see Section 16.1.2.1)

Table 2: Flow chart: pharmacokinetics and pharmacodynamics ¹⁷

PK and PD ^a	Visit 1	Visit 2			Treatment day 2			Visit 3			Treatment day 4 to 7			Visit 4
Rivaroxaban treatment days	Screen day -10 to day 1	Treatment day 1			Treatment day 2			Treatment day 3			Treatment day 4 to 7			Day 8
Rivaroxaban administration		1 st dose	2 nd dose	3 rd dose	1 st dose	2 nd dose	3 rd dose	1 st dose	2 nd dose	3 rd dose	1 st dose	2 nd dose	3 rd dose	
PK/PD time points		0.5 to 3 hr post dose	7 to 8hr post dose					0.5 to 3 hr post dose	7 to 8hr post dose					10-16 hr after last dose at day 7
Obtain blood sample for PK ^b		•	•					•	•					
Obtain blood sample for PD ^c			•					•						• ^d

hr = hour(s), PD = pharmacodynamics, PK = pharmacokinetics
^a The approximate total blood volume taken per child for PK/PD is 6.6 mL. Always draw the PD sample as the last sample.
^b Blood volume per PK sample is approximately 0.6 mL; total blood volume for all PK samples is 2.4 mL.
^c Blood volume per PD sample is approximately 1.4 mL; total blood volume for all PD samples is 4.2 mL.
^d If continued treatment with anticoagulants is necessary, administer the anticoagulant after last sample is taken for rivaroxaban.

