5.1 Method of treatment allocation

5.1.1 Rivaroxaban regimen - amended

Age- and body weight-adjusted rivaroxaban will be administered three times daily approximately 8 hours apart as oral suspension. The oral suspension will be administered immediately before or (early) during feeding.³¹

Originally, the study started with a b.i.d. regimen. Rivaroxaban was well tolerated in the 5 children treated according to the b.i.d. regimen and there were no bleeding events. Furthermore, no symptomatic recurrent venous thromboembolic complications occurred. Repeat imaging of the thrombosis in two children with a persistent thrombosis at the start of

²⁷ Exclusion criterion 9 was modified via Amendment 1 (see Section 16.1.2.3)

²⁸ Exclusion criterion 10 was modified via Amendment 1 (see Section 16.1.2.3)

²⁹ Exclusion criterion 12 was modified via Amendment 4 (see Section 16.2.2.9)

³⁰ This section was modified via Amendment 4 (see Section 16.2.2.10)

³¹ Throughout the complete section t.i.d. dosing was introduced via Amendment 5 (see Section 16.3.2.5)

rivaroxaban treatment showed normalization and substantial regression of the thrombosis, respectively, after the 7-day treatment with rivaroxaban.

However, PK results of the first 5 children enrolled with the b.i.d. regimen indicate lower rivaroxaban exposure ($AUC_{ss,24h}$) and C_{trough} concentrations than initially expected by the PK model. Based on these observations, the Data Monitoring Committee recommended to change the dosing regimen from a b.i.d. (approx. 12-hour intervals) to a t.i.d. (approx. 8-hour intervals) schedule applying the same individual doses previously administered twice daily. This recommendation was endorsed by the steering committee.

Following implementation of Amendment 5, children will be dosed according to the t.i.d. schedule (according to [Table 3](#)). The 50% increase of the total daily dose will increase the exposure, and the shortening of the dosing interval from 12 to 8 hours (t.i.d. schedule) aims to increase the C_{trough} concentrations.

If a rivaroxaban individual dose was missed, the t.i.d. administration schedule with approx. 8-hour intervals should be resumed without compensating for the missed dose.

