6.12 PK/PD assessment - amended

Blood samples will be taken for PK/PD measurements. The number and volume of PK/PD blood samples represents the minimum amount of blood needed for adequate analysis (sparse sampling approach). The following blood samples will be taken: ⁴⁷

- two post-dose PK samples at visit 2
- one post-dose PD sample at visit 2
- two post-dose PK sample at visit 3
- one post-dose PD sample at visit 3
- one post-dose PD sample at visit 4

The exact time of rivaroxaban dosing and PK/PD blood sampling will be documented in the eCRF. If, for any reason, PK/PD samples are taken outside of the pre-specified time window, the exact time that the sample was taken should be recorded and not the time of the time window.

The use of low dose heparin and tissue plasminogen activator to maintain catheter patency is acceptable. However before collecting PK/PD samples, the catheters need to be flushed with saline. In addition, if PK/PD samples are drawn through a central line, a small amount of blood needs to be drawn and discarded, before collecting the PK/PD sample in order to avoid dilution of the PK/PD sample with saline that remains in the central line.

The prothrombin time, activated partial thromboplastin time and anti-factor Xa activity (anti Xa) will be used to assess the pharmacodynamic effects after administration of the study drug.

Detailed information about the handling and labeling of the samples will be provided in the laboratory manual.

The data obtained from the blood samples taken will be analyzed.

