7.8 Determination of sample size

At least 8 children are planned to be enrolled in the study. For the area under the curve (AUC), a geometric coefficient of variation (geom. CV) of about 40% was observed in adults, and was also observed in study 12892 in the age group 12 to 18 years (n=9). In the age cohort 6 to <12 years, an even smaller geometric coefficient of variation was observed. Although it is expected from the model that the variability will be higher in neonates and infants, the exact numbers remain unclear. The sample size of 8 subjects will yield an exploratory 90% confidence interval for the geometric mean AUC-estimate between 50% and 200% of the estimate, provided the geometric coefficient of variation does not exceed 138%, which would be more than a tripling of the variability observed in adolescents. If the geometric coefficient of variation will be 80%, the exploratory 90% confidence interval for the geometric mean AUC-estimate would be located between 62% and 161% of the estimate.

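### SAP 6.4 summarises individual popPK-derived parameters with no shrinkage check, so the reported SD and CV tend to understate between-child variability.

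*SAP*

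**What the plan says.** SAP 6.4 first tabulates measured rivaroxaban concentrations by sampling interval. The listed statistics include arithmetic mean, SD, CV, geometric mean, "geometric standard deviation (re-transformed standard deviation of the logarithms) and CV", minimum, median and maximum. It then turns to model output: "If applicable, pharmacokinetic characteristics derived via popPK modeling", apart from tmax, "will be summarized by the statistics mentioned above". For tmax it plans minimum, maximum, median and frequency counts.

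The data behind the model are thin. Protocol Table 2 states: "Blood volume per PK sample is approximately 0.6 mL; total blood volume for all PK samples is 2.4 mL". SAP Table 2 shows the older twice-daily schedule but gives the same total ("total blood volume for all PK samples is 2.4 mL"). Protocol 6.12 says that the number and volume of samples "represents the minimum amount of blood needed for adequate analysis (sparse sampling approach"). SAP 5.1 lets a child into the PK analysis with one sample, and protocol 17.1.1 uses only values above the quantification limit for PK parameters.

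Protocol 7.6 describes the modelling in one sentence. Neither it nor SAP 6.4 mentions shrinkage, the model-estimated between-child variance, or which parameters are fixed. Protocol 7.8 bases the sample size on an "exploratory 90% confidence interval for the geometric mean AUC-estimate" and says that the variability to expect in neonates and infants is unclear.

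**The concern.** A minimum, a median and frequency counts make sense only if there is one model-derived value per child. Such values are a compromise between the child's own few concentrations and the population value. The less a child's data say, the closer the estimate lies to the centre. The SD and CV of these values are then smaller than those of the children's true parameters. A measured concentration is not affected in this way, so the same statistics do not mean the same thing in the two tables.

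With four samples split between days 1 and 3, AUC cannot be read from the data directly, and SAP 6.4 offers no other route to it. AUC is the quantity that protocol 7.8 uses for the sample size, and its variability in this age group is one of the things the trial can teach. A table of individual estimates with no shrinkage beside it would make exposure look more uniform than it is, and a reader could not tell by how much.

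**Working it through.** **Inputs from the documents.** PK samples per child: 2.4 mL / 0.6 mL = 4 (protocol Table 2; SAP Table 2 agrees). n = 8, 90% confidence, geometric CV of 138%, 80% and about 40% in adults (protocol 7.8).

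**Assumed input.** The standard error (SE) of a child's log-AUC as estimated from that child's data alone: 0.2, 0.4 or 0.6. The documents give no residual error, SE or shrinkage.

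**Step 1: reproduce protocol 7.8.** On the log scale, sigma = sqrt(ln(1 + CV²)), and the limits are exp(±t × sigma / sqrt(8)), where t = 1.895 (7 degrees of freedom).
- CV 138%: sigma = 1.033, limits 50.1% and 199.7% (stated 50% and 200%).
- CV 80%: sigma = 0.703, limits 62.4% and 160.2% (stated 62% and 161%).

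The plan's figures reproduce within rounding.

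**Step 2: shrinkage implied by the assumed SE.** Let R = sigma² / (sigma² + SE²). The SD of the individual estimates is sqrt(R) × sigma, so SD shrinkage is 1 − sqrt(R). Example at CV 80%, SE 0.6: R = 0.495 / (0.495 + 0.36) = 0.579 and shrinkage = 1 − 0.761 = 0.239.

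**Step 3: apparent CV and naive interval.** Apparent CV = sqrt(exp(R × sigma²) − 1). The naive interval uses sqrt(R) × sigma in the Step 1 formula. If the population mean is re-estimated from the same children, the mean of the individual estimates keeps the full sampling error of the data while the SD is shrunk. Coverage of a nominal 90% interval is then P(|T| < 1.895 × R), with T on 7 degrees of freedom.

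| True CV | SE of log-AUC (assumed) | SD shrinkage | Apparent CV | Naive 90% interval | Coverage |
|---|---|---|---|---|---|
| 80% | 0 | 0% | 80% | 62%–160% | 90% |
| 80% | 0.2 | 4% | 76% | 64%–157% | 88% |
| 80% | 0.4 | 13% | 67% | 66%–151% | 81% |
| 80% | 0.6 | 24% | 58% | 70%–143% | 69% |
| 40% | 0 | 0% | 40% | 77%–129% | 90% |
| 40% | 0.2 | 11% | 35% | 80%–126% | 82% |
| 40% | 0.4 | 31% | 27% | 84%–120% | 61% |
| 40% | 0.6 | 46% | 21% | 87%–115% | 40% |

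The coverage formula was checked by simulation (200,000 samples of n = 8 at CV 80%). At SD shrinkage of 20%, 30% and 50% the formula gives 73.5%, 61.6% and 35.0%; the simulation gave 73.5%, 61.5% and 35.0%.

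The direction is the same in every row: apparent spread is too small. Shrinkage is milder when true variability is high, because each child's data then carry more weight relative to the population value.

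**The case against.** The strongest reply is that the SAP is descriptive throughout, lists no confidence interval in 6.4, and makes no decision on the CV. That stands. The interval in protocol 7.8 is a planning illustration labelled exploratory, and nothing says it will be built from individual estimates. The last two columns of the table therefore show what would follow if it were, not a flaw in a planned analysis.

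Second, the sentence is conditional, and the SAP does not name the estimator. That also stands, though the requested statistics point to one value per child, and AUC has no other source in the SAP.

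Third, shrinkage may be small: at a true CV of 80% and an SE of 0.2 it is 4%. This is fair, but the plan contains no check that would show whether the trial is in that case.

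Fourth, measured concentrations are tabulated separately for each sampling interval, with individual plots at actual times. That gives unshrunk summaries of the concentrations, including trough-type samples, but not of AUC.

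A reader might also infer that the geometric mean AUC is pulled back toward the earlier model, given that "PK results of the first 5 children enrolled with the b.i.d. regimen indicate lower rivaroxaban exposure" than that model had expected. The documents do not support this. It would follow only if typical values were held fixed or carried a strong prior, and nothing says so. Protocol 5.1.1 points the other way: the lower exposure was seen with the same number of samples and led to a change of regimen.

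**Conclusion.** The concern holds in a limited form. The SD, CV and geometric CV planned in SAP 6.4 for model-derived parameters tend to understate between-child variability, and the plan has nothing that would reveal the extent. The direction rests on the values being individual estimates conditional on sparse data, which the text implies but does not state. The size rests wholly on assumed errors: a true geometric CV of 80% would appear as roughly 76% to 58%, and one of 40% as roughly 35% to 21%. One-sample children or values below the quantification limit could make it worse.

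The plan cannot be said to report a wrong interval, because SAP 6.4 reports none. Nor can it be said that the mean exposure is biased. This is a reporting weakness in the primary objective that should be corrected; it does not invalidate the analysis.

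**What to change.** In SAP 6.4:
- Take between-child CV for model-derived parameters from the model's estimated random-effect variance, with its uncertainty.
- Give the population geometric mean AUC with a 90% interval from the model's parameter uncertainty, so that the quantity in protocol 7.8 has a defined source. The technique for the interval is the modeller's choice.
- Report shrinkage per parameter beside any summary of individual estimates, and label those summaries as such.
- State which model parameters are fixed, which are re-estimated, and from which data.

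SAP 4.5 already provides for an amendment or supplement. The cost is some extra wording and standard model output, with no new samples. The variability figures will be wider and less favourable, and with about eight children the variance estimate will itself be imprecise, which its uncertainty interval should show.
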